13.4.1. Serious Adverse Events and Suspected Unexpected Serious Adverse Reactions

All SAEs must be reported immediately and no later than 24 hours of investigator awareness to the sponsor medical monitor via the AE and SAE eCRFs. Investigators should adhere to their country or region requirements for the reporting timeframe, which may not allow any delay. All additional follow-up evaluations of the SAE must be reported to BioCryst or its designee as soon as they are available by amending these eCRFs.

In the event the eCRF system is not functioning, the reporting of an SAE must not be delayed. Sites will have SAE report forms (electronic Word document) that can be completed and emailed to the below recipients. As soon as the eCRF system is functioning, that particular SAE must be entered into the SAE eCRF. All follow-up information on the SAE should be reported via the SAE eCRF. The eCRF system automatically sends SAE notifications to the following email address:

Email: [contact]

Immediate reporting should allow BioCryst to take the appropriate measures to address potential new risks in a clinical study. Therefore, the initial report should be submitted by the investigator within a very short period of time and under no circumstances should this period exceed 24 hours following awareness of the SAE.

The follow-up report should allow BioCryst to determine whether the SAE requires a reassessment of the benefit-risk profile of the study drug/IMP in clinical study, if the relevant information was not already available and provided in the initial report.

Investigators or designees at each site are responsible for retaining copies of all suspected unexpected serious adverse reaction (SUSAR) reports (initial and follow-up) and other safety information (eg, revised IB) in their investigator site files.

BioCryst shall ensure that all relevant information about SUSARs that are fatal or life-threatening is recorded and reported as soon as possible to all competent authorities, and to the applicable IECs/IRBs in any case no later than 7 calendar days after knowledge by BioCryst of such a case, and that relevant follow-up information is subsequently communicated within an additional 8 days. All other SUSARs shall be reported to the competent authorities concerned and to the IECs/IRBs, as applicable according to local regulations, as soon as possible but in no case later than 15 calendar days of first knowledge by BioCryst. BioCryst or designee shall also

inform the investigator. Although acute kidney injury is considered an expected event (see Section 6.11 of the IB), the event will be reported in an expedited manner.

13.4.2. Pregnancy

Any female subject who becomes pregnant during the course of the study should have study drug/IMP discontinued immediately and must be followed through the end of the pregnancy. While pregnancy is not considered an AE, all cases of fetal drug exposure via the parent as a study participant (including partners of study participants) are to be reported immediately to BioCryst or its designee. Consent from study partners who become pregnant will be obtained prior to reporting any details of the pregnancy. Information related to the pregnancy must be given on a "Pregnancy Notification and Outcome" form that will be provided by the sponsor or its designee so that the pregnancy may be followed, and an outcome determined. Any AEs or SAEs experienced by a pregnant subject are to be reported as directed in Section 13.1.3. Any complications reported in a subject's pregnant partner should be reported on the Pregnancy Notification and Outcome form. All pregnancies must be followed to outcome, which occurs when an infant is delivered (live or still born), there is fetal demise, or there is an abortion (spontaneous or induced). Abortion (spontaneous or induced), fetal demise, and still birth, along with congenital abnormalities in the newborn, should be reported as separate SAEs.

13.5. Adverse Event Management

The investigator (or qualified designee) will grade clinically significant events and laboratory abnormalities (if considered AEs) as detailed in Section 13.2. Grade 3 and 4 clinically significant laboratory abnormalities should be confirmed by repeat testing and before any contemplated study drug discontinuation, unless such a delay is not consistent with good medical practice.

13.5.1. Potential Drug-induced Liver Injury: Monitoring, Evaluation, and Discontinuation Criteria

All treatment-emergent ALT elevations $> 3 \times \text{ULN}$ should be confirmed, preferably within 72 hours, with repeat assessment of ALT, AST, total bilirubin, ALP, prothrombin time/INR, and complete blood count with differential. These may be repeated at a local laboratory as long as the results are reported to the investigator when available and the investigative site contacts the subject to ascertain any symptoms.

Subjects with potential drug-induced liver injury (pDILI) meeting this ALT elevation must be assessed to determine whether study drug must be withheld or discontinued per Sections 7.4.1. In addition, any potentially contributing medications, supplements, or over-the-counter medications that are not medically necessary should be discontinued if medically feasible.

Discontinuation of treatment should be considered for any of the following, and should be discussed with the sponsor medical monitor, considering the benefit: risk of discontinuing BCX9930:

[figure not shown]
- ALT or AST $> 8 \times ULN$
- ALT or AST > 5 \times ULN for more than 2 weeks

- ALT or AST > 3 × ULN and total bilirubin > 2 × ULN (unless there is evidence that
 the increase in bilirubin is due to Gilbert's syndrome) or INR > 1.5 in the absence of
 warfarin therapy
- ALT or AST > 3 × ULN with the appearance of fatigue (over baseline fatigue), nausea, vomiting, right upper quadrant pain or tenderness, fever, rash, and/or eosinophilia (> 5%)

If subjects are asymptomatic with no other pertinent laboratory abnormality, study drug may be continued under close observation. Transaminases, total bilirubin, ALP, and INR should be repeated at least twice weekly. Frequency of retesting can decrease to once per week or less if abnormalities stabilize or the study drug has been discontinued and the subject is asymptomatic. Additionally, several other items should be considered, including obtaining a more detailed history of symptoms and prior or concurrent diseases; obtaining a history of concomitant use of nonprescriptive medications, herbal and dietary supplements, alcohol intake, recreational drug use, special diets; evaluation for acute viral hepatitis A, B, C, D, and E and potentially other serologies; evaluation for others as clinically indicated including alcoholic and autoimmune hepatitis, non-alcoholic steatohepatitis (NASH), and biliary tract disease.

If Hy's Law criterion is met and assessed as probably or definitely related to study drug by the investigator, then study drug must be discontinued per treatment discontinuation criterion in Section 7.4.1. The investigator should contact the sponsor medical monitor for a discussion regarding the event and assessment. If medically indicated, the investigator can discontinue the subject immediately and follow up with the sponsor within 24 hours.

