7.4. Individual and Study Termination Criteria

7.4.1. Study Drug Treatment Discontinuation Criteria

A subject will be permanently withdrawn from BCX9930 for any of the following reasons:

• Pregnancy in a female subject.

^{† =} Clinical Benefit Assessment

T = Safety Follow-up Visit: 28 ± 3 days after last dose of BCX9930 for all subjects

F = Safety Follow-Up

- Emergence of an AE, including a laboratory abnormality, or other unacceptable toxicity that, in the judgment of the investigator, compromises the ability of the subject to continue study-specific procedures or it is considered not to be in the subject's best interest to continue due to an altered benefit-risk profile.
- Intercurrent illness or the emergence of a new medical condition that would, in the judgment of the investigator, affect assessments of clinical status to a significant degree.
- Treatment-emergent alanine aminotransferase (ALT) or aspartate aminotransferase (AST) > 3 × ULN combined with either laboratory abnormalities indicative of significant hepatic toxicity (ie, meeting Hy's law, total bilirubin > 2 × ULN OR with an INR > 1.5) or with symptomatology of acute hepatitis (ie, severe fatigue, nausea, vomiting, right upper quadrant pain and tenderness, fever, rash, and/or eosinophilia [> 5%]) and assessed by the investigator as probably, or definitely related to BCX9930 treatment.
- Treatment-emergent increase in sCr \geq 3 × ULN (confirmed by repeat testing) without any other potential cause of renal dysfunction
- In the investigator's opinion it is in the best interest of the subject to discontinue from further dosing.
- Invasive meningococcal infection or any serious invasive bacterial infection that occurs after BCX9930 is initiated.
- Subject request to discontinue for any reason.
- Subject noncompliance (eg, protocol deviation), as assessed by the sponsor or investigator, to be detrimental to study or subject benefit-risk profile.
- Discontinuation at the request of the sponsor, relevant competent authority, or the governing institutional review board (IRB), research ethics board (REB), or independent ethics committee (IEC) (collectively referred to as "ethics committee").

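### Protocol 13.5.1 triggers the prompt liver panel and the withhold/discontinue assessment on ALT alone, although the stopping rules they serve use ALT or AST

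*Protocol*

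**What the plan says.** Protocol 13.5.1 opens with the trigger: "All treatment-emergent ALT elevations", with the limit set at 3 × ULN. The instruction for these is that they "should be confirmed, preferably within 72 hours, with repeat assessment of ALT, AST, total bilirubin, ALP, prothrombin time/INR, and complete blood count with differential". Its second paragraph makes the follow-on step mandatory for the same subjects: "Subjects with potential drug-induced liver injury (pDILI) meeting this ALT elevation must be assessed to determine whether study drug must be withheld or discontinued", with a pointer to 7.4.1.

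The rules behind that trigger are wider.

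- **Mandatory withdrawal (7.4.1):** "Treatment-emergent alanine aminotransferase (ALT) or aspartate aminotransferase (AST) > 3 × ULN combined with either laboratory abnormalities" of significant hepatic toxicity, or with symptoms of acute hepatitis. The list of symptoms includes eosinophilia above 5%. The event must also be "assessed by the investigator as probably, or definitely related to BCX9930 treatment".
- **Consider discontinuation (13.5.1):** there are four bullets, at 8 × ULN, at 5 × ULN for more than two weeks, at 3 × ULN with bilirubin or INR, and at 3 × ULN with symptoms or eosinophilia. All four name ALT or AST.

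For asymptomatic subjects with no other relevant laboratory abnormality who stay on drug, 13.5.1 adds: "Transaminases, total bilirubin, ALP, and INR should be repeated at least twice weekly". A blood count is not in that list.

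**The concern.** The trigger is narrower than the rules it feeds. A subject with AST above 3 × ULN and ALT at or below it can meet 7.4.1 or one of the bullets. Yet the text that would prompt confirmation, the full panel and a formal assessment does not mention that subject. Neither document gives a reason for treating the two enzymes differently at this one step. The SAP liver table (10.4) treats them alike.

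What is at stake is consistency of safety follow-up between sites. After an ALT rise the investigator has an instruction. After an AST rise of the same size, the speed of confirmation, the differential count and the formal assessment rest on judgment. Eosinophilia cannot be judged without a differential, so one qualifying finding could go unmeasured for a time. The visits most exposed fall in the first 12 weeks, when the extra laboratory measurements include monitoring for hepatic toxicity (Protocol 5.5.3.3).

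**Working it through.** The plan gives no figure on this point to reproduce. The check compares the texts and then counts schedule days.

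**Step 1. Follow an isolated AST rise (AST > 3 × ULN, ALT ≤ 3 × ULN) through the protocol.**

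| Element | Source | Reached by an AST-only rise? |
|---|---|---|
| Confirmatory panel, preferably within 72 hours | 13.5.1, first paragraph | No; ALT only |
| Mandatory withhold/discontinue assessment | 13.5.1, second paragraph | No; ALT only |
| Mandatory withdrawal rule | 7.4.1 | Yes |
| Consider-discontinuation bullets | 13.5.1 | Yes |
| Repeat transaminases, bilirubin, ALP, INR | 13.5.1, twice-weekly retest | Probably; it follows the ALT-or-AST bullets |
| Repeat of clinically significant Grade 3–4 values | 13.5 | Yes if graded so; no panel or time target |
| Return-visit set for hepatic events | 11.3.5 | Yes if asked to return; the blood tests listed are chemistry and PK |
| Blood count with differential | none of these texts | Not named |

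**Step 2. Count the visits where this matters most.** In Protocol Table 3 the post-baseline visits through Week 12 are Weeks 1, 2, 3, 4, 5, 6, 7, 8, 10 and 12, which makes 10. All have chemistry. Weeks 3, 5, 6, 7 and 10 have no haematology or coagulation: 5 of 10. Adding Weeks 16, 20 and 24 gives 5 of 13 through Week 24. At the other 5 visits (8 through Week 24), INR and the count are drawn with the chemistry, so only the explicit trigger is missing.

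**Step 3. Time to the next scheduled count.** The visit days and windows come from Protocol 11.3.4 and 11.3.5. The nominal gap is the next haematology day minus the visit day. The shortest gap pairs the latest first visit with the earliest next one, and the longest gap does the reverse.

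| Visit (day) | Next count (day) | Nominal | With windows |
|---|---|---|---|
| Week 3 (22 ± 1) | Week 4 (29 ± 1) | 29 − 22 = 7 | 28 − 23 = 5 to 30 − 21 = 9 |
| Week 5 (36 ± 3) | Week 8 (57 ± 3) | 57 − 36 = 21 | 54 − 39 = 15 to 60 − 33 = 27 |
| Week 6 (43 ± 3) | Week 8 (57 ± 3) | 57 − 43 = 14 | 54 − 46 = 8 to 60 − 40 = 20 |
| Week 7 (50 ± 3) | Week 8 (57 ± 3) | 57 − 50 = 7 | 54 − 53 = 1 to 60 − 47 = 13 |
| Week 10 (71 ± 3) | Week 12 (85 ± 3) | 85 − 71 = 14 | 82 − 74 = 8 to 88 − 68 = 20 |

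These gaps are upper limits, because they assume that the investigator orders nothing after seeing the AST result.

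**Step 4. What the other tests do meanwhile.** A twice-weekly retest gives INR about every 7 / 2 = 3.5 days (84 hours), close to the preferred 72 hours for ALT. Scheduled chemistry repeats AST and bilirubin after 7 days from Weeks 3, 5, 6 and 7 (29 − 22, 43 − 36, 50 − 43, 57 − 50) and after 14 days from Week 10 (85 − 71). The differential is the one panel item that neither route supplies.

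**The case against.** The strongest reply is that little remains once the other text is read. Section 7.4.1 binds for AST without any trigger in 13.5.1, and it cannot be applied without assessing the subject. Even for ALT, the panel is recommended rather than required. Results are reviewed as received, and local laboratories may be used when a safety concern needs a fast answer (12.11.5). The procedures in 11.3.5 are a stated minimum. Potential drug-induced liver injury is an event of special monitoring with no ALT restriction (13.1.4). For the missing differential to change a decision, eosinophilia would have to be the sole qualifying finding, and mandatory withdrawal would also need probable or definite relatedness. All of this stands and limits the consequence. It does not supply an AST trigger or name a differential.

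A reader might infer four stronger points that the documents do not support.

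- *That an AST-only case cannot be withdrawn.* Section 7.4.1 names AST.
- *That INR would go unchecked.* The twice-weekly retest includes INR and is most naturally read as covering AST.
- *That the gaps in Step 3 are expected delays.* They are times to the next routine draw.
- *That 7.4.1 needs the Gilbert's and warfarin exceptions found in 13.5.1* ("the increase in bilirubin is due to Gilbert's syndrome) or INR > 1.5 in the absence of" warfarin therapy). Those exceptions sit in a consider-discontinuation bullet and do not contradict a mandatory rule. That rule requires "laboratory abnormalities indicative of significant hepatic toxicity (ie, meeting Hy's law, total bilirubin > 2 × ULN OR with an INR > 1.5", together with probable or definite relatedness. Screening also excludes INR above 1.4 and bilirubin above 1.5 × ULN, with an allowance for Grade 1 elevation due to Gilbert's syndrome (exclusion 11). Adding the exceptions would loosen a mandatory stopping rule for little gain.

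**Conclusion.** The point holds as a wording mismatch in a safety procedure. For an isolated AST rise, two things are missing: an explicit trigger for prompt confirmation and formal assessment, and any named blood count with differential. The practical exposure is concentrated at 5 of the 10 post-baseline visits through Week 12, with the upper limits shown above.

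The priority is low to moderate. The conclusion assumes that the twice-weekly retest applies to AST. If it does not, the same upper limits apply to INR. The documents give no rate of isolated AST rises, so the number of subjects affected cannot be estimated; it is assumed to be low.

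No sample size, estimate or summary table changes. SAP 4.1 records that development stopped before any subject enrolled under Protocol Version 4.0, so the point concerns the protocol text and any later protocol that reuses it.

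**What to change.** Make two edits in Protocol 13.5.1:

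1. First sentence: begin *All treatment-emergent ALT or AST elevations > 3 × ULN*, leaving the panel and the 72-hour preference as they are.
2. Second paragraph: replace *this ALT elevation* with *this ALT or AST elevation*.

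Leave 7.4.1 unchanged. The cost is a few extra repeat draws in subjects with isolated AST above 3 × ULN. The visit schedule, sample size and analysis are unaffected.

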13.5.3. SARS-CoV-2 and COVID-19

As complement inhibitors do not inhibit cellular or humoral immunity, BCX9930 is not expected to increase the risk of contracting COVID-19 following infection with SARS CoV-2 or to increase the risk of severe illness with COVID-19. However, all study activity will be conducted in accordance with relevant local, regional, and national guidance around COVID-19. In order to minimize the risk of COVID-19 transmission, additional procedures or assessments (which may include but are not limited to symptom assessment, temperature, viral RNA testing, and antibody testing) may be implemented at the discretion of the investigator beyond those required for this protocol.

13.6. Overdose

To date, there is no experience with overdose of BCX9930. Healthy subjects received BCX9930 at a dose of 2000 mg administered as single doses and as multiple once-daily doses for 3 days in Study 101 with no clinically significant safety concerns. In the event that study personnel become aware of an overdose of BCX9930 that is associated with an AE, both the overdose and the resultant event should be reported as AEs. Overdose without any symptoms (ie, AEs) does not need to be reported as an AE but would be captured as a protocol deviation. If overdose occurs with or without associated AEs, subjects should undergo clinical and laboratory monitoring, as appropriate for their clinical condition and, if indicated, should receive clinically indicated supportive therapy.

See also Section 13.1.3.

13.7. Data Monitoring Committees

An independent, program-wide DMC, which will include a nephrologist and other members with relevant expertise, will regularly review the cumulative safety data from this study, as well as the accumulating, long-term safety data across all BCX9930 studies.

Prior to opening enrollment to subjects with an eGFR \geq 30 mL/min/1.73 m², a minimum of at least 4 subjects with an eGFR \geq 50 mL/min/1.73 m² must have completed at least 4 weeks of BCX9930 dosing. After the minimum number of subjects and duration of dosing are met, the DMC may recommend expanding enrollment to include subjects with an eGFR

 \geq 30 mL/min/1.73 m² based on an acceptable renal safety profile of BCX9930. Enrollment under existing inclusion for subjects with an eGFR \geq 50 mL/min/1.73 m² will not be paused during this DMC review.

In the event that a new clinically significant safety signal emerges, a meeting of the DMC may be convened by the sponsor to evaluate risk to subjects and recommend appropriate actions. Based on the data presented, a decision will be made as to whether to halt the study, to continue dosing, or to continue dosing with provisions introduced into the protocol via substantial amendment.

The specific responsibilities and composition of the DMC are outlined in a separate DMC charter.

A NRMWG will review and advise on subjects with treatment-emergent increases in sCr and other renal events. The specific responsibilities and composition of the NRMWG are outlined in a separate charter.

14. STATISTICS

14.1. Hypotheses

This is a POC study to estimate the therapeutic potential of BCX9930 administered in subjects with C3G, IgAN, or PMN. Post-baseline measurements will be assessed against their applicable baseline measurements.

14.2. Sample Size Considerations

No formal power or sample size calculations are planned to determine the sample size for each cohort. The proposed sample size of approximately 14 subjects per cohort should provide an estimate of uPCR reduction up to 52 weeks to estimate the safety and therapeutic potential for BCX9930 in these renal indications and inform sample sizes for future studies of BCX9930.

Several recent Phase 2 studies that evaluated investigational products with similar or identical mechanisms of action as BCX9930 enrolled 5 to 7 subjects with C3G per study and reported reductions in proteinuria after treatment durations ranging from 2 to 48 weeks (unpublished data).

No sample size re-estimations are planned.

14.3. Stratification

No stratifications are planned.

14.4. Statistical Methods

A detailed statistical analysis plan (SAP) will be developed to describe the methods of analyses and summaries, including all endpoints, time points, populations, missing data, etc. Deviations from the analyses outlined in the SAP will be described in the clinical study report (CSR). A summary of the methods for interim analyses based on ongoing review of individual subject

safety and preliminary efficacy data for each treatment cohort, if conducted, will be provided in the SAP.

14.4.1. Analysis Populations

The analysis populations are defined below.

14.4.1.1. Full Analysis Set Population

The Full Analysis Set (FAS) population is defined as all subjects who receive at least one dose of study drug. The FAS population will be used as the primary population for demographics, baseline characteristics, safety, and efficacy analyses.

14.4.1.2. Pharmacokinetic Population

The PK population will include all FAS population subjects for whom PK concentration data are available.

14.4.1.3. Pharmacokinetic Substudy Population

The PK substudy population will include all FAS population subjects for whom serial PK concentration data are available and PK parameters can be estimated.

14.4.1.4. Pharmacodynamic Population

The PD population will include all FAS population subjects for whom at least 1 pre-dose and at least 1 post-dose PD/biomarker measurement can be obtained. This population will be used for all PD/biomarker analyses.

14.4.2. General Considerations for Data Analysis

In general, descriptive summaries will include n, mean, standard deviation, median, minimum, and maximum for continuous variables and n and percentage for categorical variables. Summaries will be presented by treatment cohort and, where appropriate, by visit or pooled across the treatment cohorts.

All individual subject data will be listed as measured. All statistical summaries and analyses will be performed using SAS® software (SAS Institute, Cary, North Carolina, USA).

